#### **7.2.1.1 Dose Modification and Toxicity Management for Immune-related AEs Associated with Pembrolizumab Monotherapy, Coformulations or IO Combinations**

AEs associated with pembrolizumab monotherapy, coformulation, or IO combination exposure may represent an immune-related response. These irAEs may occur shortly after the first dose or several months after the last dose of pembrolizumab monotherapy, coformulation, or IO combination treatment and may affect more than one body system simultaneously. Therefore, early recognition and initiation of treatment is critical to reduce complications. Based on existing clinical study data, most irAEs were reversible and could be managed with interruptions of pembrolizumab monotherapy, coformulation, or IO combination administration of corticosteroids and/or other supportive care. For suspected irAEs, ensure adequate evaluation to confirm etiology or exclude other causes. Additional procedures or tests such as bronchoscopy, endoscopy, skin biopsy may be included as part of the evaluation.

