Diarrhea / Colitis	Grade 2 or 3	Withhold	
 
• Administer corticosteroids (initial dose of 1-2 mg/kg prednisone or equivalent) followed by taper
 
	
 
• Monitor participants for signs and symptoms of enterocolitis (ie, diarrhea, abdominal pain, blood or mucus in stool with or without fever) and of bowel perforation (ie, peritoneal signs and ileus)
 
• Participants with <math>\geq</math>Grade 2 diarrhea suspecting colitis should consider GI consultation and performing endoscopy to rule out colitis
 
• Participants with diarrhea/colitis should be advised to drink liberal quantities of clear fluids. If sufficient oral fluid intake is not feasible, fluid and electrolytes should be substituted via IV infusion.
 

	Recurrent Grade 3 or Grade 4	Permanently discontinue		

irAEs	Toxicity Grade (CTCAEv4.0)	Action With Pembrolizumab Monotherapy, Coformulations or IO Combinations	Corticosteroid and/or Other Therapies	Monitoring and Follow-up
AST / ALT Elevation or Increased Bilirubin	Grade 2 a	Withhold	
 
Administer corticosteroids (initial dose of 0.5-1 mg/kg prednisone or equivalent) followed by taper
 
	
 
Monitor with liver function tests (consider weekly or more frequently until liver enzyme value returned to baseline or is stable)
 

	Grade 3 b or 4 c	Permanently discontinue	
 
Administer corticosteroids (initial dose of 1-2 mg/kg prednisone or equivalent) followed by taper
 
	
T1DM or Hyperglycemia	New onset T1DM or Grade 3 or 4 hyperglycemia associated with evidence of $\beta$ -cell failure	Withhold d	
 
Initiate insulin replacement therapy for participants with T1DM
 
Administer anti-hyperglycemic in participants with hyperglycemia
 
	
 
Monitor participants for hyperglycemia or other signs and symptoms of diabetes
 

Hypophysitis	Grade 2	Withhold	
 
Administer corticosteroids and initiate hormonal replacements as clinically indicated
 
	
 
Monitor for signs and symptoms of hypophysitis (including hypopituitarism and adrenal insufficiency)
 

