#### **7.2.2.4 Dose Modifications for Lenvatinib Management of Hepatotoxicity**

Regular monitoring of liver function tests (eg, alanine transaminase [ALT], aspartate transaminase [AST], bilirubin levels) should be conducted as detailed in the SoA in Section 2. If signs/symptoms indicating liver injury occur, instructions contained in [Table 8](#) should be followed. Appropriate supportive care should be provided together with close monitoring. If hepatic failure occurs, lenvatinib must be discontinued.

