#### **7.2.2.11 Dose Modifications for Overlapping Toxicities**

Based on the known toxicity profiles of pembrolizumab and lenvatinib, certain treatment-related AEs are uniquely associated with one drug versus the other. For example,

hypertension, arterial thrombotic events, proteinuria, and hemorrhagic events are known risks for lenvatinib treatment, while immune-related AEs are risks for pembrolizumab treatment. However, certain AEs, such as such as diarrhea, hypothyroidism, and liver enzyme elevation, may be initially considered attributable to either study drug. Therefore, evaluation of attribution is important for determining the study drug most likely related to the AE, or an alternative etiology, and subsequently proper clinical management. The following aspects should be considered:

1. Timing of AE onset

Since lenvatinib is dosed daily and continuously due to a relatively short half-life (28 hours), and pembrolizumab is dosed Q3W due to a long half-life, lenvatinib can be interrupted to assess whether an AE improves/resolves with dechallenge (ie, interruption of treatment) based on the following two scenarios:

- If an AE is identified during a treatment cycle (ie, between 2 pembrolizumab doses), only lenvatinib dose interruption is needed.
- If an AE is identified at the beginning of a treatment cycle, lenvatinib can be interrupted and dosing of pembrolizumab should be held.

If the participant recovers from an AE in response to lenvatinib interruption (ie, positive dechallenge), the event is more likely to be related to lenvatinib. Otherwise, after excluding other alternative explanations, an immune-related AE should be considered.

2. Severity of AE

If an AE is suspected to be treatment-related and is severe/life threatening at the time of onset or is rapidly worsened, action including interrupting both drugs and initiating treatment with a corticosteroid (with exception of hypothyroidism, T1DM) and other supportive care should be taken promptly.

3. Participants receiving the combination therapy (pembrolizumab + lenvatinib) must discontinue study therapy if any of the following occur:

- 1) ALT or AST >5 X ULN for more than 2 weeks.  
Pembrolizumab will have already been permanently discontinued per [Table 6](#), but lenvatinib may be administered at a reduced dose by the time this criterion is met and must be permanently discontinued immediately.
- 2) ALT or AST >3 X ULN and (TBL >2 X ULN or INR >1.5).  

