Although [Table 6](#) advises pembrolizumab to be withheld (interrupted), and [Table 8](#) advises lenvatinib to have no dose modification or a reduction, if this criterion is met, both drugs must be permanently discontinued immediately.

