# **8 Discontinuation/Withdrawal Criteria**

## **8.1 Discontinuation of Study Treatment**

Discontinuation of study treatment does not represent withdrawal from the study.

As certain data on clinical events beyond study treatment discontinuation may be important to the study, they must be collected through the participant's last scheduled follow-up, even if the participant has discontinued study treatment. Therefore, all participants who discontinue study treatment prior to completion of the protocol-specified treatment period will still continue to participate in the study as specified in Section 2 - Schedule of Activities and Section 9.10.3.

Participants may discontinue study treatment at any time for any reason or be dropped from the study treatment at the discretion of the investigator should any untoward effect occur. In addition, a participant may be discontinued from study treatment by the investigator or the Sponsor if study treatment is inappropriate, the trial plan is violated, or for administrative and/or other safety reasons. Specific details regarding procedures to be performed at study treatment discontinuation are provided in Section 9.1.9 – Withdrawal/Discontinuation.

A participant must be discontinued from study treatment but continue to be monitored in the study for any of the following reasons:

- The participant or participant's legally acceptable representative requests to discontinue study treatment.

- ALT or AST elevation meeting the following criteria:
  - ALT or AST  $>5 \times$  ULN for more than 2 weeks  
Pembrolizumab will have already been permanently discontinued per [Table 6](#), but lenvatinib may be administered at a reduced dose by the time this criterion is met and must be permanently discontinued immediately.
  - ALT or AST  $>3 \times$  ULN and (TBL  $> 2 \times$  ULN or INR  $> 1.5$ )  
Although [Table 6](#) advises pembrolizumab to be withheld (interrupted), and [Table 8](#) advises lenvatinib to have no dose modification or a reduction, if this criterion is met, both drugs must be permanently discontinued immediately.
- The participant interrupts pembrolizumab, MK-1308, or MK-4280 administration for more than 12 consecutive weeks for an irAE or for more than 3 consecutive weeks for administrative reasons, unless approved with written documentation from the Sponsor.

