- The participant interrupts lenvatinib administration for more than 28 consecutive days, unless approved with written documentation from the Sponsor.
- Clinical conditions described in Section 7.2 Dose Modification
- The participant has a medical condition or personal circumstance which, in the opinion of the investigator and/or sponsor, placed the participant at unnecessary risk from continued administration of study treatment.
- The participant has a confirmed positive serum pregnancy test.
- The participant has a positive urine drug screen at any time during the course of the study.
- Confirmed radiographic disease progression outlined in Section 9.2.1.4 (after obtaining informed consent addendum and Sponsor communication, the investigator may elect to continue treatment beyond disease progression).
- Any progression or recurrence of any malignancy, or occurrence of another malignancy that requires active treatment
- Noncompliance with study treatment or procedure requirements
- Any study treatment-related toxicity specified as a reason for permanent discontinuation as defined in the guidelines for dose modification due to AEs in Section 7.2.
- Completion of 35 treatments (approximately 2 years) with pembrolizumab. Combination treatment with MK-1308 or MK-4280 will be discontinued upon completion of the 35th cycle of pembrolizumab. For the lenvatinib combination arm, if a participant completes 35 infusions of pembrolizumab, they may continue with lenvatinib alone until disease progression or toxicity.

Discontinuation of treatment may be considered for participants who have attained a confirmed CR by local investigator assessment and have been treated for at least 8 cycles and received at least 2 cycles beyond the date when the initial CR was declared.

For participants who are discontinued from study treatment but continue to be monitored in the trial, all visits and procedures, as outlined in the SoA, should be completed.

Discontinuation from study treatment is “permanent.” Once a participant is discontinued, he/she shall not be allowed to restart study treatment.

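### In the lenvatinib arm, the INR limb of a mandatory permanent liver stop has no test tied to it and no provision for participants on anticoagulants

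*Combined protocol and SAP*

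**What the plan says.** Section 7.2.2.11 gives the scope: "Participants receiving the combination therapy (pembrolizumab + lenvatinib) must discontinue study therapy if any of the following occur". The second criterion listed is "ALT or AST >3 X ULN and (TBL >2 X ULN or INR >1.5"). The text then states that it overrides the dose tables: Table 6 would only withhold pembrolizumab, and although Table 8 "advises lenvatinib to have no dose modification or a reduction, if this criterion is met, both drugs must be permanently discontinued immediately". Section 8.1 repeats the criterion with the same consequence, "if this criterion is met, both drugs must be permanently discontinued immediately", and closes the door afterwards: "Once a participant is discontinued, he/she shall not be allowed to restart study treatment".

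On testing, Table 3 puts one mark in the PT/INR and aPTT row, at screening. A note printed there asks for Day 15 samples in Cycles 1 and 2 in this arm, and allows further coagulation tests when clinically indicated in participants on anticoagulants. Section 7.2.2.4 says "Regular monitoring of liver function tests (eg, alanine transaminase [ALT], aspartate transaminase [AST], bilirubin levels) should be conducted as detailed in the SoA". The AST/ALT row of Table 6 says "Monitor with liver function tests (consider weekly or more frequently until liver enzyme value returned to baseline or is stable"). Section 7.2.1.1 adds "For suspected irAEs, ensure adequate evaluation to confirm etiology or exclude other causes". Appendix 4 obliges the investigator to arrange supplemental measurements that are medically indicated or that the sponsor requests.

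On entry, Table 4 limits INR or PT and aPTT to 1.5 x ULN but waives the limit under anticoagulation within therapeutic range. It allows ALT/AST up to 5 x ULN with liver metastases.

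**The concern.** A mandatory rule should rest on a value that the protocol makes available when the rule has to be applied, and its threshold should not be crossed by a condition that the eligibility criteria accept. The INR limb falls short on both counts.

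If no INR is drawn, half of the second part of the criterion goes unassessed. If an INR is drawn in an anticoagulated participant, both drugs may have to stop because of the anticoagulant's effect on the test. The second error cannot be undone, because Section 8.1 does not allow a restart.

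**Working it through.** No figure in the plan has to be reproduced. The check sets the texts side by side; the arithmetic is only for size.

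1. **Logic of the criterion.** Stop if A and (B or C), where A is ALT/AST >3 x ULN, B is TBL >2 x ULN and C is INR >1.5. If B is false, the criterion reduces to A and C. If C has not been measured, it cannot be evaluated.

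2. **Which values are on hand.** Chemistry, which includes ALT, AST and bilirubin (Table 13), is marked in Table 3 at every cycle, at discontinuation and at safety follow-up. PT/INR is marked at screening. The extracted table does not settle whether the Day 15 note covers PT/INR; if it does, it adds C1D15 and C2D15 only. Neither reading ties an INR to a raised ALT/AST.

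3. **Where the INR limb decides** (TBL not above 2 x ULN, normal baseline):
   - ALT/AST >3 to 5 x ULN: Table 6 withholds pembrolizumab, and the hepatotoxicity row of Table 8 begins at Grade 3. INR decides the permanent stop of both drugs.
   - ALT/AST >5 x ULN for up to 2 weeks: Table 6 has already ended pembrolizumab, and Table 8 says hold or discontinue lenvatinib. INR decides only whether ending lenvatinib is mandatory.
   - ALT/AST >5 x ULN for more than 2 weeks: the first criterion of Section 7.2.2.11 applies and INR is irrelevant.

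4. **Trace at ALT 4 x ULN, normal baseline:**
   - TBL 2.1 x ULN, any INR: both drugs stop permanently.
   - TBL 1.0 x ULN, INR 1.6: both stop permanently.
   - TBL 1.0 x ULN, INR 1.2: not met. Pembrolizumab is withheld and lenvatinib may be interrupted.
   - TBL 1.0 x ULN, no INR: cannot be assessed.

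5. **Anticoagulated participant with liver metastases.** Take ALT 4 x ULN and an INR above 1.5 within therapeutic range at entry. Table 4 admits this participant (4 is not above 5, and the INR limit is waived). If nothing changes on treatment, ALT is 4/4 = 1.0 x baseline. Footnote a of Table 6 starts Grade 2 above 3 x baseline when the baseline is abnormal, so Table 6 asks for no action. Under Sections 7.2.2.11 and 8.1, A and C are both true, and both drugs must stop for good. The exclusion criteria and prohibited medications do not bar anticoagulants, and the Table 3 note expects such participants.

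6. **Size.**
   - Planned arm with equal allocation: (66 + 66 + 66 + 90)/3 = 96. At the arm caps: 25 + 25 + 25 + 40 = 115.
   - Assume 5% to 15% exceed 3 x ULN (not in the documents): 0.05 x 96 = 4.8 to 0.15 x 115 = 17.25, so about 5 to 17 over the whole arm.
   - Assume further that 2% to 5% of those have an anticoagulant-driven INR above 1.5 (also not in the documents): 0.02 x 4.8 = 0.1 to 0.05 x 17.25 = 0.9 participants.

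**The case against.** The strongest reply is that the protocol already leads the investigator to an INR. Appendix 4 imposes a duty, not just a permission, to do what is medically indicated. Section 7.2.1.1 asks for adequate evaluation, Appendix 2 permits extra tests, and a stopping rule that names INR arguably implies checking it. This stands in part: a careful investigator would draw one. But none of these texts names INR as a test to run, and the duty turns on judgement, while the rule that depends on it leaves none.

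Other safeguards also count. Hepatic failure ends lenvatinib under Section 7.2.2.4 and Table 8, ALT/AST >5 x ULN for more than 2 weeks ends both drugs, Table 6 withholds pembrolizumab from Grade 2, and Section 7.2.2.11 allows lenvatinib to be interrupted. A reader might infer that participants with liver injury go unmanaged without an INR. The documents do not support that; what is left open is this one permanent stop.

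A reader might also count the liver texts that do not name INR and take their silence as proof of an oversight. That is weak evidence. Table 13 leaves out PT/INR even though Table 3 requires it at screening, the list in Section 7.2.2.4 is by example, Table 6 lists no panel, and the definition in Section 9.3.7 needs bilirubin of at least 2 x ULN.

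On anticoagulants, an entry limit and a stopping rule serve different purposes and need not match. Stopping whatever the cause is the cautious choice with a drug that carries a bleeding risk. An anticoagulated participant's INR can also rise from liver injury. This stands as an argument against a blanket exemption. It does not explain a rule that an eligible participant can meet on the first day without any change in the liver.

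**Conclusion.** Both parts hold, at minor severity. INR decides a mandatory, irreversible stop whenever ALT/AST exceeds 3 x ULN with bilirubin not above 2 x ULN and the first criterion is not met, and no text ties an INR to that event. The INR limb also has no provision for anticoagulants, so the anticoagulant alone can complete the criterion in an eligible participant with liver metastases.

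A reader might infer damage to the efficacy result. The documents do not support that: every treated participant stays in the ASaT denominator for ORR whether or not treatment is stopped.

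The numbers are small and rest on assumed rates: about 5 to 17 participants in the INR-testing range over the whole arm, and probably fewer than one affected by the anticoagulant problem. Most of this may be past. Pembrolizumab ends after 35 administrations, about 2 years. The current text is Amendment 09 of April 2025, and Amendment 08 already provides for an extension study. The documents do not say how many participants are still on the combination.

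**What to change.** In Sections 7.2.2.11 and 8.1 and in the Table 3 PT/INR note, require a local PT/INR together with bilirubin whenever ALT/AST exceeds 3 x ULN in a participant on pembrolizumab + lenvatinib.

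State that in participants on therapeutic anticoagulation the INR limb is read against the participant's own baseline or therapeutic range, so that it is met by a rise that the anticoagulant does not explain. Leave the bilirubin limb as it is. The exact clinical wording is for the sponsor to decide.

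The cost is amendment wording in two sections and one schedule note, one extra local blood test in a few participants (about 5 to 17 over the whole arm on the assumed rates, fewer from now on), and somewhat more judgement in anticoagulated participants.

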**7.2.2.12 General Guidelines for Holding Periods of Lenvatinib Due to Procedures**

If the study participant is receiving treatment with lenvatinib and requires surgery during the study, the stop time and restart time of lenvatinib should be as follows:

- For minor procedures: Stop lenvatinib at least 2 days before the procedure and restart it at least 2 days after, once there is evidence of adequate healing and no risk of

bleeding. Needle biopsies (fine needle aspirations and core needle aspiration) are usually considered minor procedures.

- For major procedures: Stop lenvatinib at least 1 week (5 half-lives) prior to surgery and then restart it at least 1 week after, once there is evidence of adequate healing and no risk of bleeding. It is up to the investigator to determine if it is a major or minor procedure. Usually, a major procedure implies general anesthesia.

### **7.3 Method of Treatment Assignment**

Initially, all eligible participants will be randomly allocated and will receive a treatment/randomization number. The treatment/randomization number identifies the participant for all procedures occurring after treatment allocation/randomization. Once a treatment/randomization number is assigned to a participant, it can never be re-assigned to another participant.

A single participant cannot be assigned more than 1 treatment/randomization number.

Treatment randomization will occur centrally using an interactive voice response system/integrated web response system (IVRS/IWRS).

#### **7.3.1 Adaptive Randomization**

Study participants will first be assigned to a biomarker-defined group ( $\text{GEP}^{\text{low}}\text{TMB}^{\text{low}}$ ,  $\text{GEP}^{\text{low}}\text{TMB}^{\text{hi}}$ ,  $\text{GEP}^{\text{hi}}\text{TMB}^{\text{low}}$ , or  $\text{GEP}^{\text{hi}}\text{TMB}^{\text{hi}}$ ) based on screening test results of TMB and GEP assays.

Due to the different start time of three combination treatments, unequal randomization ratio may be used first, and then randomization schedules will be adjusted to equalize treatment arm enrollment per biomarker-defined group depending on the time of introducing the delayed combination treatments in order to meet study analysis milestones.

For each biomarker-defined group, the first interim analysis will occur after at least 10 participants in each treatment combination have at least 12 weeks of follow-up. After the first interim analysis, participants' response data will be closely monitored throughout the study, and the subsequent interim analyses may be performed with a minimum of 2 additional participants achieving 12 weeks of follow-up for each combination therapy that still remains in the study. At each interim analysis, there will be an opportunity to drop individual treatment combinations within biomarker-defined groups or entire biomarker-defined groups for futility or safety. As long as any biomarker-defined group and treatment combination are retained in the study, enrollment will continue with equal randomization to the remaining treatment arms (see details in Section 10.7).

#### **7.3.2 Stratification**

Treatment randomization will be stratified based on the assigned biomarker-defined group based on screening test results of TMB and GEP assays.

### **7.4 Blinding**

This is an open-label trial; therefore, the Sponsor, investigator and participant will know the treatment administered.

## **7.5 Preparation/Handling/Storage/Accountability**

### **7.5.1 Dose Preparation**

Details on preparation and administration of pembrolizumab, MK-1308, MK-4280, and lenvatinib are provided in the Pharmacy Manual.

The rationale for selection of doses to be used in this trial is provided in Section 3.3 – Background. There are no specific calculations or evaluations required to be performed in order to administer the proper dose to each participant.

### **7.5.2 Handling, Storage and Accountability**

The investigator or designee must confirm appropriate temperature conditions have been maintained during transit for all study treatment received and any discrepancies are reported and resolved before use of the study treatment.

Only participants enrolled in the study may receive study treatment and only authorized site staff may supply or administer study treatment. All study treatments must be stored in a secure, environmentally controlled, and monitored (manual or automated) area in accordance with the labeled storage conditions with access limited to the investigator and authorized site staff.

The investigator, institution, or the head of the medical institution (where applicable) is responsible for study treatment accountability, reconciliation, and record maintenance (ie, receipt, reconciliation, and final disposition records).

For all trial sites, the local country Sponsor personnel or designee will provide appropriate documentation that must be completed for drug accountability and return, or local discard and destruction if appropriate. Where local discard and destruction is appropriate, the investigator is responsible for ensuring that a local discard/destruction procedure is documented.

The trial site is responsible for recording the lot number, manufacturer, and expiry date for any locally purchased product as per local guidelines unless otherwise instructed by the Sponsor.

The investigator shall take responsibility for and shall take all steps to maintain appropriate records and ensure appropriate supply, storage, handling, distribution and usage of study treatments in accordance with the protocol and any applicable laws and regulations.

